Review and expungement of criminal record. Criminal records are a major barrier to competitive employment in adults with a history of illicit drug use. To help participants prepare for competitive employment, we may collaborate with community partners (e.g., Maryland Legal Aid) who offer free legal assistance to participants in Phases 1 and 2. This assistance typically consists of determining eligibility for expungement, processing petitions for expungement of criminal records, and other free services approved by the legal team. Participants are notified by research staff that legal assistance is available, and that participation is voluntary. We may collect data to describe and evaluate the expungement process so we may better understand legal barriers to employment in adults with a history of illicit drug use. The data we would collect are the types of offenses participants have on their public records (i.e., records available to potential future employers), the number of convictions on record, which records are eligible or ineligible for expungement, whether petitions for expungement are filed by the legal team, whether petitions for expungement are granted or require a hearing, and how long it takes for participants to have their records expunged. We may publish an article to describe the expungement process and de-identified data of our participants. All data that we collect and publish on the criminal histories of our participants will be data that are publicly available.

Random Assignment

Participants (N = 120) will be randomly assigned to an IPS Only (Control) or IPS Plus Abstinence-Contingent Wage Supplements group. A computerized urn randomization procedure (Wei & Lachin, 1988) will be used to balance groups on three baseline characteristics that may influence outcome: (1) percentage of the three monthly urine samples collected prior to random assignment that are positive for cocaine (\geq rolling median, Y/N); (2) percentage of the three monthly urine samples collected prior to random assignment that are positive for opiates (\geq rolling median, Y/N); and (3) completed high school or obtained a GED (Yes/No). Participants will be stratified by cocaine and opiate use because drug use at random assignment should predict abstinence from opiates and cocaine and possibly employment during the intervention evaluation period. High school completion or GED should be associated with employment

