
To gain verified and objective records of employment, we may get an objective measure of each participant's employment history by getting each participant's earnings history using federal Form SSA-7050-F4 (10-2016) UF, REQUEST FOR SOCIAL SECURITY EARNINGS INFORMATION. Participants and research staff will complete this form and have the participant's earnings history sent to our research unit. Our research unit will pay for the costs of this service. We may request these documents one or more times. We will take the following steps to protect this sensitive information in our study databases (see also Section 8b): (1) when storing a completed form, we will redact name, date of birth, and social security number from the written document and label the document with an ID number; (2) keep paper copies in a locked file cabinet in a locked office and never keep documents out while unattended by research staff; (3) only enter relevant information into the database (i.e., information about when participants worked, how much they earned, and what type of employment they had); and (4) maintain a confidentiality certificate from the NIH. The risks associated with collecting this information are explained on the consent form.

a. Study duration and number of study visits required of research participants.

Participants will be invited to attend Phase 1 of the therapeutic workplace every weekday for 3 months. Participants in the immediate-work group will attend for 4 hours every weekday. Participants in the delayed work group will be asked to come to the workplace every day for a brief visit (30 minutes or less) to complete study measures for the first 3 weeks and then for the full 4 hours for the remainder of the 3 month period of Phase 1. All participants that report to be assessed at the end of Phase 1 will be randomly assigned to the primary study groups and offered Individual Placement and Support for 1 year. The IPS intervention is designed to promote employment in competitive community workplaces. All participants will be invited to participate in an intake assessment to determine eligibility and characterize the population. Outcome assessments will be conducted every 30 days throughout the 3-month abstinence initiation period, every 30 days throughout the 12-month intervention evaluation period after random assignment, and then at 3, 6, 9 and 12 months after the end of the intervention evaluation period.

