The primary outcome measures will be analyzed with a longitudinal logistic regression model using GEE (Diggle et al., 2002). We used Liu and Liang (1997) to determine the total N required to detect differences between groups with 80% power. The adjacent figure shows the total number of participants (N) that would be required to detect a difference of 15% between the IPS Only and the IPS Plus Abstinent-Contingent Wage Supplement with the 12 monthly assessments. The adjacent figure shows possible percentages for the IPS Only group because that value affects the sample size required. Fifteen percent is smaller than any difference in any Therapeutic Workplace study in which we promoted cocaine abstinence in methadone patients. This difference is also smaller than any difference between Control and IPS groups in the percentage of participants that become employed. Based on this, we need a maximum of 120 participants (horizontal dashed line) to detect a difference between the IPS Only and the IPS Plus Abstinent-Contingent Wage Supplement groups of 15% or more on each primary outcome.

Statistical Analyses

Main analysis. All measures assessed repeatedly over time will be analyzed with a longitudinal logistic regression model. Within-person correlated outcomes will be handled using generalized estimating equations (GEE; Zeger et al., 1988). Measures assessed once will be analyzed using logistic regression. The magnitude of effect for both logistic regression and GEE will be expressed using odds ratios with 95% CI. Analyses will include all randomized participants as intent-to-treat, and will be adjusted for pre-specified covariates used for stratification (Pocock et al., 2002). Tests will be two-sided and p-values <.05 will be considered significant.

Moderator analyses. We will conduct analyses to identify variables that moderate the outcomes of our two primary outcome measures, employment and drug (opiates and cocaine) abstinence. We will examine differences in efficacy as a function of two variables assessed prior to random assignment by including interaction terms in our regression models: 1) Percentage of urine samples negative for opiates and cocaine at the three monthly urine samples collected prior to random assignment. 2) Completed high

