The GMA component of the study will address important questions raised by previous findings at the NIDA IRP (Epstein and Preston, 2012). The implication of those findings was that work might cause reductions in stress and drug craving during treatment for addiction. But before drawing treatment recommendations or policy recommendations from that finding, we need corroborative information collected under more controlled conditions. This Therapeutic Workplace study will provide that. The result should be more reliable recommendations.

Risk/Benefit Ratio. Overall, there are limited risks associated with this protocol above normal daily living. There are considerable potential benefits to the participants in this study, to people living with the participants, and to the community at large. Overall, the risk/benefit ratio appears highly favorable.

10. Payment and Remuneration

All incentives in this study will be provided by giving participants reloadable credits and adding incentives to the card when earned. Restrictions can be placed on these cards to restrict where they can be used to make purchases. We have been using these reloadable credit cards in our ongoing research and they have proved attractive to participants and convenient for staff to manage.

Phase 1 Training Incentives. All participants will be invited to attend the Therapeutic Workplace for 4 hrs every weekday for about 3 months (12 weeks), where they can earn about \$10/hr for participating in our job skills or health education training program.

Some participants may get jobs in the community before their participation in the therapeutic workplace ends (i.e., before Phase 1 ends) and may have to stop attending our workplace to maintain their outside employment. Thus, we may offer wage supplements to participants who get jobs during Phase 1. Under the wage supplement procedure, participants would be able to earn a wage supplement for all hours that they work in a community job (up to our current maximum of 20 hours per week) as long as they continue to meet their drug abstinence requirements. The amount of the wage supplements will be equivalent to the current base pay hourly wage that participants can earn for working in the workplace. In total, participants will be able to earn \$2,400 in Phase 1 for training in the workplace and/or for wage subsidies. The amounts will vary depending on each participant's productivity and the number of hours worked.

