Phase 2 Abstinence-Contingent Wage Supplements. Participants in the Abstinence-Contingent Wage Supplement group will be able to earn wage supplements of up to \$8 per hour for up to 40 hours per week for 52 weeks. In total, participants in the Abstinence-Contingent Wage Supplement group will be able to earn up to \$16,640 in wage supplements.

Participant payment for assessments. Assessments will be conducted for all participants at intake to determine eligibility and characterize the population, immediately prior to random assignment, periodically throughout the 3-month abstinence initiation period, every 30 days throughout the 12-month intervention evaluation period after random assignment, and then at 3, 6, 9 and 12 months after the end of the intervention evaluation period. Participants will be paid \$30 for the intake and pre-random assignment assessments, \$30 for each monthly assessment during the 3-month abstinence initiation period and the 12-month intervention evaluation period, and \$50 for the each assessment conducted 3, 6, 9 and 12 months after the end of the intervention evaluation period. In total, participants will be able to earn up to \$710 for completing the assessments in this study.

Participant referral fees. As in our previous studies, participants will have the optional opportunity to earn incentives for referring people who are interested in the study. If a referral attends the initial

screening appointment and completes the necessary assessments, the participant who referred the person will receive up to \$20. If a referred person enrolls in the main study, the participant who referred the person will receive up to \$40 for making the referral.

GMA-related payments. Participants can earn:

- \$ 5 / day (\$2.50 for each drug/urine day) if urine is negative for cocaine and heroin/opioids and no self-reported use for either drug on smartphone OR if urine is positive for either cocaine or heroin/opioids and there is self-reported use (on smartphone) of the drug for which the participant tested positive (i.e., if urine positive for cocaine, must have self-reported cocaine use, etc.). Payment is only made for corresponding urines and smartphone self-reports; no payment is made for non-corresponding data. When a urine sample is missed or no data is able to be retrieved from the smartphone and there is no evidence for a malfunctioning smartphone is found, there will be no payment for that day.

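### Employment at randomisation is neither balanced nor adjusted for, although participants can hold jobs by then; this costs precision on the co-primary employment outcome but does not bias it

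*Combined protocol and SAP*

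**What the plan says.** Section 5 makes unemployment an inclusion criterion, and section 9 says that all participants will be unemployed when the study starts. Random assignment to the two primary groups follows Phase 1, about three months later.

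Section 10 (Phase 1 Training Incentives) recognises that some participants may find community jobs before Phase 1 ends, and continues: "Thus, we may offer wage supplements to participants who get jobs during Phase 1". That supplement depends on meeting the abstinence requirements, is paid at the workplace base wage and covers up to 20 hours a week. Section 4.a does not exclude those who have found work: "All participants that report to be assessed at the end of Phase 1 will be randomly assigned to the primary study groups". After randomisation, the IPS Only group receives no wage supplement (section 4, Individual Placement and Support (IPS) Only Group).

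The urn procedure is "used to balance groups on three baseline characteristics that may influence outcome": cocaine-positive urines, opiate-positive urines, and high school or GED. The main analysis (section 7.c) "will be adjusted for pre-specified covariates used for stratification", so these three are the only covariates. The two baseline moderators are earlier urine results and high school/GED.

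The co-primary employment outcome (section 7.a) is self-reported employment, yes or no, at each of 12 monthly assessments. Section 10 (Participant payment for assessments) lists an assessment "immediately prior to random assignment, periodically throughout the 3-month abstinence initiation period", and section 4 schedules assessments every 30 days during Phase 1.

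**The concern.** The plan treats its two primary outcomes differently. For drug abstinence, each participant's own pre-randomisation results are used for balance and for adjustment, because drug use at random assignment is expected to predict later abstinence. For employment, the corresponding baseline value is left out, and the main employment predictor in the model is high school/GED. No reason is given.

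A job held at randomisation counts as employment in the following months, in either arm, for as long as it lasts. With about 60 people per arm, the arms can differ by chance in the number who start with a job, and the planned model has no term for it. Variation between people that one baseline item could explain stays in the standard error.

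Interpretation is also affected. For someone without a job at randomisation, the comparison is about finding work and then keeping it. For someone already employed and supplemented, it is about keeping work while a supplement either continues on new terms or ends. The plan does not describe this second situation or say how many people are in it.

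**Working it through.** **The plan's own figure.** Section 7.c gives a maximum of 120 participants for 80% power to detect a 15-point difference over 12 monthly assessments, two-sided at 0.05. The repeated-binary formula with exchangeable correlation ρ and 1:1 allocation is

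n per arm = (1.960 + 0.842)² × (p₁q₁ + p₂q₂) × (1 + 11ρ) / (12 × 0.15²).

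The requirement is largest at rates of 42.5% and 57.5%, where p₁q₁ + p₂q₂ = 0.48875 and n per arm = 14.21 × (1 + 11ρ). Sixty per arm corresponds to ρ of about 0.29; ρ = 0.5 would give a total of 186. The text does not state ρ, and the figure is not shown in the copy reviewed, so 120 cannot be confirmed uniquely. Nothing here shows it to be wrong.

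**Inputs for the check, all assumed**
- Share employed at randomisation, f: 5%, 10% or 20%. The nearest figure in the documents is about 20% working full-time after earlier Therapeutic Workplace participation (section 3), which is a different time point.
- 60 per arm (the allocation ratio is not stated).
- Employment at 25% of monthly assessments in those without a job at randomisation, and 40 points more in those with one.
- ρ = 0.5, with ρ = 0.29 as a second case.

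**Formulas**
- SD of the chance imbalance = √(2f(1−f)/60).
- Shift in the employment difference from a 1-SD imbalance = 0.40 × that SD.
- Overall rate m = 0.25 + 0.40f.
- Variance of a person's 12-month rate, V = m(1−m) × (ρ + (1−ρ)/12). At ρ = 0.5 the last factor is 0.5417.
- Part explained by baseline employment, E = f(1−f) × 0.40².
- Standard error (SE) of the arm difference = √(2V/60) unadjusted and √(2(V−E)/60) adjusted.

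**Results at ρ = 0.5** (imbalance, shift and SEs in percentage points)

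| f | Imbalance SD | Shift per SD | V | E | E/V | SE unadjusted | SE adjusted |
|---|---|---|---|---|---|---|---|
| 5% | 4.0 | 1.6 | 0.1068 | 0.0076 | 7% | 5.97 | 5.75 |
| 10% | 5.5 | 2.2 | 0.1115 | 0.0144 | 13% | 6.10 | 5.69 |
| 20% | 7.3 | 2.9 | 0.1198 | 0.0256 | 21% | 6.32 | 5.60 |

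The 95% half-width (1.96 × SE) falls from 11.7, 12.0 or 12.4 points to 11.3, 11.2 or 11.0.

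The shift is not an additional error. At f = 10%, √(5.69² + 2.19²) = 6.10, which is the unadjusted SE. Chance imbalance is therefore already inside the planned confidence interval, and adjustment removes it.

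**Second case, ρ = 0.29.** The last factor in V becomes 0.3492. The SE goes from 4.79 to 4.52 (f = 5%), 4.90 to 4.38 (10%) and 5.07 to 4.15 (20%). The relative gain is larger because less of the variance is left unexplained.

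**Bias and type I error.** A simulation used 4,000 trials per setting, 60 per arm, an assumed monthly job loss of 0.12 and job finding of 0.05. Each person's 12-month rate was analysed with and without baseline employment. With no treatment effect and f from 5% to 30%, the mean difference was about zero. Type I error was 0.044 to 0.051 unadjusted and 0.047 to 0.050 adjusted.

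With job finding raised to 0.105 in the intervention arm, adjustment raised power from 0.76 to 0.79 (f = 5%), 0.71 to 0.76 (10%) and 0.60 to 0.68 (20%). The fall in power down that series is partly dilution, because the simulated effect acted only on finding a job. Adjustment does not restore that part. For scale, if only those not employed could gain 15 points, the overall difference would be 15 × (1−f) = 14.25, 13.5 or 12.0 points.

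**The case against.** The strongest reply is that randomisation already does the work. Jobs carried over from Phase 1 are equal between arms in expectation, the planned test keeps its level, and the planned interval allows for imbalance. That is correct. A reader might infer that the employment result is biased, or that shifts of a few points add to its stated uncertainty; neither follows.

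A second reply is that retention belongs to the aim. The abstract offers supplements to those who obtain and maintain employment, and IPS includes support in the job. Counting every month employed is therefore a legitimate outcome, and combining entry with retention is not a mistake. This stands too. What remains is that no planned analysis shows the two apart, although the monthly records would allow it.

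A third reply concerns exposure before randomisation. A reader might conclude that some controls receive the test intervention in Phase 1. The terms differ: base-wage pay for up to 20 hours a week in Phase 1, against up to $8 an hour for up to 40 hours, payments for job-search tasks and a reset rule afterwards. After induction, maximum Phase 1 pay already depends on negative urines for everyone. The documents support a description of who was supplemented, not a claim of contamination.

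Finally, the numbers may be small. Section 10 says only that participants may get jobs and that supplements may be offered; section 3 calls earlier use of such supplements occasional. That points to the lower shares and a modest gain.

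**Conclusion.** The omission is clear from the text; its size is not. Participants can be employed, and supplemented on Phase 1 terms, when randomised, and the plan neither balances nor adjusts for this on an outcome it probably predicts strongly. The consequence is lost precision and an unadjusted chance imbalance. On the ρ = 0.5 assumptions, adjustment cuts the variance of the employment difference by about 7%, 13% or 21% if 5%, 10% or 20% are employed at randomisation. These figures rest on the assumed share, the 40-point gap, the 25% rate and the correlation, none of which is in the documents.

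The documents do not support excluding employed participants from randomisation, calling the primary analysis invalid, or disputing the sample size on this ground. The point is worth acting on because the remedy is nearly free and matches what the plan already does for drug use.

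**What to change.** By a dated amendment before the comparative analysis:

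1. Add employment (yes/no) at the last assessment before random assignment as a covariate in the primary employment GEE model, alongside the three stratification factors. Show the currently planned model as a sensitivity analysis.
2. Report employment at randomisation and receipt of a Phase 1 wage supplement, by arm.
3. Add a supporting analysis in those not employed at randomisation: 114, 108 or 96 of 120 at shares of 5%, 10% or 20%.
4. Describe those already employed without a formal effect estimate. They would number 6, 12 or 24 in all, about 3, 6 or 12 per arm.

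The section on COVID-19 procedures speaks of completing the remaining assessments, so randomisation has probably closed and a further urn factor would come too late. If the comparative analysis has already been done, the adjusted model should be labelled post hoc. Because no blinding is described, the amendment should state its date and reason.

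The cost is small. The assessments are already scheduled, but the team should confirm that the last one before randomisation recorded employment, which section 10 does not say. The adjusted odds ratio becomes conditional on baseline employment and will differ somewhat from the one now planned. If few participants were employed, the gain is modest, and reporting that number would settle the matter.
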